2 ANALYSIS POPULATIONS

The following populations for analyses are defined. Unless otherwise specified, these populations will be applicable for both safety run-in and core phase parts. The participants included in the safety run-in part, if fulfilling the inclusion criteria of the core phase part and if the planned dose and dosing schedule are the same as in core phase will be included in the analyses of core phase.

Table 4 - Populations for analyses

Population	Description
Screened	All participants who have been given the informed consent form.
Enrolled	All participants who have given their informed consent and have been allocated to an intervention (by IRT) regardless of whether the intervention was received or not.
Exposed	All participants who have given their informed consent and received at least one dose (even incomplete) of IMP (SAR444245 or pembrolizumab).
Population without trial impact (disruption) due to COVID-19	All exposed participants: 
without any critical or major deviation related to COVID-19and who did not permanently discontinue treatment due to COVID-19and who did not permanently discontinue study due to COVID-19.
Efficacy	All participants from the exposed population with at least one evaluable post-baseline tumor assessment or who permanently discontinued study treatment.
DLT-evaluable ^a	All exposed participants in safety run-in part who have been treated and observed for DLT observation period (defined in the individual substudy). Any participants who have experienced a DLT during DLT observation period will also be DLT-evaluable.
Response evaluable	All participants from the efficacy population with at least one baseline and one evaluable post-baseline tumor assessments. Participants who died from disease progression before any TA will also be response-evaluable.
Pharmacokinetic (PK)	All participants from the exposed population with at least 1 PK concentration available after the first dose of study intervention.
ADA	All participants from exposed population with at least 1 ADA result (positive, negative or inconclusive) after the first dose of study intervention.
Pharmacodynamics (PDy)	All participants from the exposed population with at least 1 PDy (biomarker) parameter assessed after the first dose of study intervention.

^a The dose-limiting toxicity (DLT) observation period is 21 days for Cohort A, and 28 days for Cohort C1.

Participants exposed to study intervention before or without being enrolled will not be considered enrolled and will not be included in any analysis population. The safety experience of these participants will be reported separately.

For any participant enrolled and treated more than once, only the data associated with the first enrollment will be used in any analysis population. The safety experience associated with any later enrollment will be reported separately.

3 STATISTICAL ANALYSES

3.1 GENERAL CONSIDERATIONS

In general, continuous data will be summarized using the number of observations available, mean, standard deviation (SD), median, minimum, and maximum. Categorical and ordinal data will be summarized using the count and percentage of participants.

The baseline value is defined as the last available value before the first administration of any of the two IMPs (SAR444245 or pembrolizumab). For participants enrolled but not treated, the baseline value is defined as the last available value before enrollment.

Unless otherwise specified, analyses will be performed by cohort, by dose level (if applicable) and overall. Participants enrolled in the safety run-in part and treated at the RP2D will be included in the analyses of the core part.

All efficacy analyses will be performed on the efficacy population. Complete response rate (CRR, for cohort A) and objective response rate (ORR, for cohort C1), as well as all other response-related efficacy endpoints will be derived using the Investigator's assessment per Lugano response criteria 2014 for all cohorts.

All safety analyses will be performed on the exposed population.

Central imaging may be done retrospectively if significant activity is observed (See [Section 3.2.3](#) for sensitivity analysis).

Confidence intervals will be two-sided 90% CI for efficacy analyses. CI will be used for descriptive purposes only, without inference.

The BOR is defined as the best overall response observed from the date of first IMP until disease progression, death, cut-off date or initiation of subsequent anti-cancer therapy, whichever occurs first.

Analysis period

The analysis period will be divided into 3 segments:

- The **pre-treatment period** is defined as the time from when the participants give informed consent to the first administration of the IMP.
- The **on-treatment period** (i.e., treatment-emergent (TE) period) is defined as the time from the first administration of IMP up to 30 days after the last administration of IMP.
- The **post-treatment period** is defined as the time from the end of the on-treatment, ie. 31 days after the last administration of IMP.

3.2 PRIMARY ENDPOINT(S) ANALYSIS

3.2.1 Definition of endpoint(s)

The primary endpoint is:

- **Cohort A**, complete response rate (CRR)
- **Cohort C1**, objective response rate (ORR)

The complete response rate (CRR) is defined as the proportion of participants who have a complete response (CR) as the best overall response per Investigator assessment (Lugano response criteria 2014).

The objective response rate (ORR) is defined as the proportion of participants who have a complete response (CR) or partial response (PR) as the best overall response per Investigator assessment (Lugano response criteria 2014).

3.2.2 Main analytical approach

The primary endpoints, CRR and ORR, will be analyzed with estimand 1 introduced in [Section 1.2.1](#). These endpoints are defined according to the following attributes:

- The endpoint complete response (CR) for cohort A
- The endpoint objective response (CR or PR) for cohort C1
- The treatment condition is SAR444245
 - in combination with pembrolizumab for Cohort A
 - in monotherapy for Cohort C1
- The analysis population is the efficacy population
- Intercurrent events (IE):
 - The new anticancer therapy IE will be handled with the “while not initiating new anti-cancer therapy” strategy; the primary endpoints will be assessed based on tumor assessments up to the time of new anticancer therapy.
 - The early IMP discontinuation IE will be handled with the “treatment policy” strategy; the primary endpoints will be assessed based on tumor assessments irrespective of the IMP discontinuation.

Population-level summary: Will include the - CRR (cohort A) and ORR (cohort C) and corresponding confidence interval using the Clopper Pearson exact method.

3.2.3 Sensitivity analysis

Central imaging reading may be done retrospectively if significant activity is observed. CRR (cohort A) and ORR (cohort C1) may be presented based on central imaging assessment, using the same estimand as for the primary analysis.

3.2.4 Supplementary analyses

ORR will be presented for the response-evaluable population.

This supplementary analysis will be provided using an estimand defined according to the following attributes:

- The endpoint is ORR.
- The treatment condition is SAR444245 in combination with/without pembrolizumab.
- The analysis population is the response-evaluable population.
- Intercurrent events and their handling strategy will be the same as for ORR estimand defined in [Section 3.2.2](#).
- Population-level summary will be the same as for ORR estimand defined in [Section 3.2.2](#).

The BOR will also be summarized with descriptive statistics.

3.3 SECONDARY ENDPOINT(S) ANALYSIS

The secondary endpoints detailed in this section are efficacy endpoints. Other secondary endpoints analyses are defined in [Section 3.6](#) (safety), [Section 3.7.1.1](#) (PK) and [Section 3.7.1.2](#) (immunogenicity).

3.3.1 Efficacy secondary endpoint(s)

3.3.1.1 *Definition of endpoint(s)*

The secondary efficacy endpoints are:

- The ORR is defined as the proportion of participants who have a CR or PR as BOR, for cohort A.
- The CRR is defined as the proportion of participants who have a CR as BOR, for cohort C1.
- The TTR is defined as the time from the first administration of IMP to the first tumor assessment at which the overall response was recorded as PR or CR determined by Investigator.

- The duration of response (DoR) is defined as the time from the first tumor assessment at which the overall response was recorded as PR or CR until progressive disease (PD) determined by Investigator, or death from any cause, whichever occurs first.
- The clinical benefit rate (CBR) is defined as the proportion of participants with clinical benefit (CR or PR as BOR, or SD lasting at least 6 months (i.e., 26 weeks or later from first IMP intake, allowing for the ± 7 days visit window for tumor assessment scheduled at 27 weeks) determined by Investigator per Lugano response criteria 2014.
- Progression free survival (PFS) defined as the time from the date of first IMP administration to the date of the first documented disease progression determined by Investigator or death due to any cause, whichever occurs first.

3.3.1.2 Main analytical approach

The ORR and CRR will be summarized using the same estimand as for primary endpoint ([Section 3.2.2](#)).

The time to response will be assessed on the subgroup of participants who have achieved objective response (CR or PR) and will be summarized using descriptive statistics.

The analyses of DoR and PFS are based on estimand 3 and 4 in [Section 1.2.1](#), These endpoints are defined according to the following attributes:

- DoR and PFS
- The treatment condition is SAR444245
 - in combination with pembrolizumab for Cohort A
 - in monotherapy for Cohort C1
- The analysis population for DoR corresponds to the subgroup of participants of efficacy population who have achieved objective response
- The analysis population for PFS is the efficacy population
- Intercurrent events (IE):
 - The new anticancer therapy IE will be handled with the “while not initiating new anticancer therapy” strategy; the primary endpoints will be assessed based on tumor assessments up to the time of new anticancer therapy.
 - The early IMP discontinuation IE will be handled with the “treatment policy” strategy; the primary endpoints will be assessed based on tumor assessments irrespective of the IMP discontinuation.
 - Two or more consecutive missing/unevaluable tumor assessments immediately before documented progression or death will be handled with the hypothetical strategy: DoR and PFS will be assessed based on tumor assessments had two consecutive tumor assessments not been missed immediately before documented progression or death.

- Population-level summary:
 - CRR and ORR will be summarized with descriptive statistics. In addition, two-sided 90% CIs calculated for CRR and ORR from Clopper Pearson exact method will be also provided.
 - Population-level summary will include the Kaplan Meier estimate of DOR and PFS at specified time points and corresponding CI. CIs for KM estimates will be estimated for each treatment group using the Kaplan Meier method and log-log approach based on a normal approximation following the Greenwood's formula. The quantiles of DOR and PFS and corresponding CI from Kaplan Meier method will also be provided; CI will be constructed using a log-log transformation of the survival function and the methods of Brookmeyer and Crowley. In the absence of disease progression or death before the cut-off date, DOR and PFS will be censored as indicated in Table 5.

Table 5 - Censoring rules for DOR and PFS

Situation	Date of progression or censoring	Outcome	Category
No baseline tumor assessments ^a	Date of first treatment intake	Censored	No baseline tumor assessments
No evaluable ^b post-baseline tumor assessments ^a	Date of first treatment intake	Censored	No evaluable post-baseline tumor assessments
Progression documented at or between scheduled visits	Date of the first tumor assessment documenting progression	Event	Documented progression
New anticancer treatment before documented progression	Date of the last evaluable tumor assessment before new treatment	Censored	New anticancer treatment
Death prior to the first planned post-baseline tumor assessment ^a	Date of death	Event	Death
Death at or between scheduled visits	Date of death	Event	Death
Death or documented progression immediately after two ^c or more missed or non-evaluable tumor assessments	Date of the last evaluable tumor assessment documenting no progression	Censored	Death or progression after two or more missed/unevaluable tumor assessments
Alive and no documented progression	Date of the last evaluable tumor assessment	Censored	Alive without documented progression

^a Not applicable for DOR.
^b Evaluable TA means an evaluation different from non-evaluable.
^c Two consecutive tumor assessments are considered as missed/non-evaluable if the duration between two consecutive tumor assessments done (non-missing) and evaluable is strictly longer than 20 weeks.

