The study Investigators (or designee) participating in the safety run-in of applicable cohorts and the Sponsor clinical team members will constitute the Study Board (SB). The SB will review clinical data on a regular basis. In order to decide dose confirmation or dose reduction on the basis of their knowledge of the safety data. Minutes of each meeting will be written by the Sponsor and distributed to all sites participating in the safety run-in. Decisions regarding final dose selection will be made during one of the SB meetings and documented in the meeting minutes.

After safety run-in dose confirmation, occurrence of any treatment related G3 or higher AE (excluding lymphocyte count decrease) not resolving within 72 hours in $>25\%$ of participants per regimen will trigger an ad hoc Data Monitoring Committee (DMC) to rapidly convene to assess safety or need to pause enrollment to allow for a safety review. The SB (during safety run-in), independent DMC (during core phase and expansion) and Sponsor can decide to stop any cohort in the event excessive toxicity (for example but not limited to excessive irAE or excessive number of G4/5 events) is observed.

Special considerations pertaining to methodology

Interactive Response Technology will be used to control recruitment, assignment per site and facilitate the handling, management, and accountability of drug supply.

The duration of the study for a participant will include:

- **Screening period:** Up to 28 days.
- **Treatment Period:** Enrolled participants will receive continuous treatment until PD, unacceptable adverse event (AE), or other full permanent discontinuation criteria as described in [Section 7](#), or completion of the maximum cycles allowed in the substudies. However, treatment beyond PD may be allowed for up to 9 weeks if the participant appears to be benefiting clinically after discussion with the Sponsor.
- **End of Treatment and Follow-up:** End of Treatment Visit will occur 30 days ± 7 days from last IMP administration or prior to initiation of further therapy. Participants will then enter the **Observation period** and will be followed differently depending on the reason leading to **End of Treatment (EOT)**:
 1. Participants who discontinue study treatment **without PD** or who **complete** the maximum cycles allowed in the substudies **without PD** (per Lugano response criteria 2014[2]), will be followed every 3 months ± 7 days from last IMP administration, for

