The initial tumor imaging FDG-PET CT and/or MRI will be performed within 28 days prior to C1D1. Scans performed as part of routine clinical management are acceptable for use as the screening scan if they are of diagnostic quality and performed within 28 days prior to the date of enrollment. On study imaging will be performed every 9 weeks (63 ± 7 days) after the date of first IMP and if clinically indicated. FDG-PET must be performed for the 9-week and 18-week on-treatment assessments. Imaging studies should follow calendar days and should not be adjusted for delays in cycle starts or extension. The same imaging technique should be used in a participant throughout the trial. After Week 45 tumor imaging should be performed every 12 weeks (84 ± 7 days) until progressive disease (PD). Brain CT/MRI will be performed if clinically indicated.

PET imaging is always required to confirm the first documented complete response (CR). If the first documented radiological CR is seen on CT scan only, a confirmatory PET scan (either FDG PET or PET-CT) should be obtained within 14 days to confirm that timepoint's response of CR. If the PET scan is not obtained within 14 days, the timepoint must be assessed as a PR, and the next scan should be done by one of the 3 methods above as soon as possible to confirm the CR. Once CR has been established by PET imaging, subsequent CR and/or PD may be followed by CT imaging only. The CT component of the PET-CT may be used in lieu of a standalone CT/MRI, only if the CT component is of similar diagnostic quality as a contrast enhanced CT performed without PET. If contrast enhanced PET-CT with diagnostic CT is not available, a standard FDG-PET must be performed, and a standalone diagnostic CT/MRI should be performed in addition to the FDG-PET scan. If independent CT and PET scanners are used, and the participant is receiving both scans on the same day, the PET must be performed prior to the CT with IV contrast so as to not compromise PET results. The PET-CT acquisition methodology (eg, administration of intravenous contrast) should remain consistent at all imaging visits for any given patient.

Bone marrow sample is mandated to confirm CR if bone marrow was involved by lymphoma or involvement is unknown prior to study treatment and as “clinically indicated” and “If bone marrow biopsy is not negative, a radiographic timepoint response (TPR) of CR at that time point would be downgraded to an overall PR”.

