Progressive disease (PD) by CT scan, with complete metabolic response (CMR) or partial metabolic response (PMR) by PET, should be reported as PD. Although the results of PET/CT are generally prioritized over CT, CT evidence of progressive disease cannot be discounted in the overall response assessment. Additionally, the Lugano PET/CT criteria for CMR and PMR require absence of new lesions. CT may, for example, reveal progressive disease in non-measurable or non-FDG avid sites (eg, ascites, bony lesions, effusions, bowel lesions). Such cases should be reported as PD. Likewise, a CT finding of progressive disease, in the context of no metabolic response on PET, is to be considered overall disease progression, rather than stable disease.

The findings of clinical (non-radiographic) progressive disease (PD) per Investigator should be considered PD:

- Clinical suspicion of disease progression at any time requires a physical examination and imaging assessments to be performed promptly rather than waiting for the next scheduled imaging assessment.
- If skin lesions are identified as a result of a physical exam, these are to be documented via the Lugano classification 2014 assessment as a physical exam, skin lesion.

Skin lesions must be histologically confirmed for lymphoma involvement and photographed including a ruler (color photography using digital camera). Response assessment of skin lesions should be performed at baseline and at the time of each radiological assessment.

Table 4 - Imaging or disease assessment collection plan

Procedure	Screening	Post-administration assessment
Bone marrow biopsy	-	As clinically indicated during the treatment period, EOT, and Follow-visit 1 ^a
Spleen measurement by PET-CT	Mandated	As clinically indicated during the treatment period, at EOT visit and Follow-up visit 1
CT/MRI (chest, abdomen, pelvis and any other locations with suspicion or evidence of disease involvement)	Mandated	Every 9 weeks and if clinically indicated until Week 45, and every 12 weeks from Week 45 until progressive disease
Brain imaging	If clinically indicated	-
FDG-PET	Mandated	As clinically indicated during the treatment period, at EOT visit and Follow-up visit 1, and must be performed for the 9-week and 18-week on-treatment assessments.

^a A reported response of CR by CT, or CMR by FDG-PET, must be confirmed by a bone marrow assessment performed within 14 days of the assessment.

Response assessment is detailed in [Table 7](#).

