Primary endpoint (estimand 3)	Duration of response (DoR)	Efficacy	
 - While not initiating new anti-cancer therapy (NAT) - Regardless of intervention discontinuation (treatment policy) - Had two or more consecutive tumor assessments not been missed/unevaluable immediately before documented progression or death (hypothetical strategy) 	
The Kaplan Meier estimate and corresponding confidence interval of DOR at specified time points.
 
The quantiles of DOR and corresponding confidence interval will be calculated from Kaplan Meier method.

[Secondary endpoint (estimand 4)]	Progression free survival (PFS)	Efficacy	
 - While not initiating new anti-cancer therapy (NAT) - Regardless of intervention discontinuation (treatment policy) - Had two or more consecutive tumor assessments not been missed/unevaluable immediately before documented progression or death (hypothetical strategy) 	
The Kaplan Meier estimate and corresponding confidence interval of PFS at specified time points.
 
The quantiles of PFS and corresponding confidence interval will be calculated from Kaplan Meier method.

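### The fixed 20-week gap for two missed scans fits only 9-weekly imaging; after Week 45, a progression found at the scheduled scan after one missed scan is censored, against the SAP's own rule

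*SAP*

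**What the plan says.** **Censoring rule.** SAP 3.3.1.2, Table 5, has a row that censors at the last evaluable assessment without progression. Its category is "Death or progression after two or more missed/unevaluable tumor assessments". Footnote c, attached to the word two in that row, says two consecutive assessments count as missed if "the duration between two consecutive tumor assessments done (non-missing) and evaluable is strictly longer than 20 weeks". No other threshold appears in the SAP.

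**Estimand.** The same section says: "Two or more consecutive missing/unevaluable tumor assessments immediately before documented progression or death will be handled with the hypothetical strategy". SAP 1.2.1, Table 3, sets the same condition for estimand 3 (DoR) and estimand 4 (PFS).

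**Imaging schedule.** Master protocol 8.1.1 images every 9 weeks (±7 days) from first IMP. It then says: "After Week 45 tumor imaging should be performed every 12 weeks" (again ±7 days). Master protocol Table 4 agrees: "every 12 weeks from Week 45 until progressive disease". Footnote q of the schedule of activities repeats this in both substudies. Under master protocol 4.1, participants who stop treatment without progression "will be followed every 3 months" (±7 days), counted from last IMP.

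**Reporting.** The SAP will give the "Kaplan Meier estimate of DOR and PFS at specified time points" but does not name the time points. The final analysis is 3 years after the last participant enters the cohort.

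**The concern.** The row, its category label and both estimands set the condition at two or more missed assessments. Footnote c turns that into one fixed gap for the whole study, although the imaging interval changes at Week 45. Once imaging is 12-weekly, a single missed scan exceeds the gap, and a real progression becomes a censored observation at the earlier scan.

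This removes late events and pushes late PFS and DoR estimates upwards. The affected period will be reached: treatment can last 35 x 3 = 105 weeks in Cohort A and 52 x 2 = 104 weeks in Cohort C1, and follow-up runs for 3 years. In cohorts of 25, few participants remain at risk late on, so one or two lost events matter there.

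The footnote also measures only the gap between two scans. It does not say how to apply the rule when the event is a death.

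**Working it through.** **1. Reproduce the 20 weeks.** The longest gap with exactly one scan missed is the sum of the two adjacent intervals plus two 1-week windows. On the 9-weekly schedule this is 9 + 9 + 2 = 20 weeks, which is the footnote's figure.

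**2. Apply the same formula to the rest of the schedule.** Scans fall at Weeks 9, 18, 27, 36, 45, then 57, 69, 81 and so on. With ±7 days at each end there are 15 x 15 = 225 in-window day combinations per pair of scans.

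| Exactly one scan missed | Nominal gap | Range | Combinations above 20 weeks |
|---|---|---|---|
| 9-weekly phase | 18 | 16–20 | 0 of 225 |
| Week 45 missed (36 to 57) | 21 | 19–23 | 189 of 225 (84%) |
| 12-weekly phase | 24 | 22–26 | 225 of 225 |
| 3-monthly, off treatment | 26 | 24–28 | 225 of 225 |

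Example: last scan at Week 57, Week 69 missed, progression at Week 81. The gap is 24 weeks. The estimand makes this an event at Week 81; footnote c censors it at Week 57.

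**3. A single longer gap does not repair it.** Two missed scans in the 9-weekly phase leave 27 weeks (25–29). A fixed 26-week cut-off would therefore let some true two-missed gaps through.

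**4. Size.** The documents give no missed-scan rate, so 5%, 10% and 15% missed at random are assumptions. I simulated 400,000 participants per scenario with exponential event times and a cut-off at Week 156, and compared footnote c with a true two-missed count. The median of 14.7 months is the protocol's figure for Hodgkin lymphoma (master protocol 2.2.1).

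| 24-month estimate, footnote c v two-missed count (%) | 5% missed | 10% missed | 15% missed |
|---|---|---|---|
| PFS, median 14.7 months, scheduled detection only | 37.5 v 36.1 | 39.3 v 36.8 | 41.6 v 38.0 |
| Same, half of progressions found at unscheduled scans | 35.2 v 34.4 | 36.2 v 34.8 | 37.4 v 35.4 |
| PFS, median 10.7 months, scheduled only | 25.9 v 24.8 | 27.5 v 25.2 | 29.5 v 26.2 |
| DoR, assumed median 18 months, scheduled only | 44.7 v 43.1 | 47.1 v 43.9 | 49.4 v 44.9 |
| Same, half unscheduled | 42.7 v 41.7 | 44.0 v 42.1 | 45.3 v 42.8 |

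The 10.7-month median follows from 46% PFS at 1 year, if exponential: 12 x ln 2 / (−ln 0.46) = 10.7. DoR runs place the response at Week 9.

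With a 14.7-month median, progressions wrongly censored per 25 participants are 0.98, 1.74 and 2.35, or 0.58, 1.05 and 1.40 with half found at unscheduled scans. Adding a scan at end of treatment and 3-monthly scans afterwards leaves the 24-month PFS excess at 1.3–3.7 points, or 0.7–2.2 with unscheduled detection. Across the 4–12 month range that the protocol gives for NHL, the excess is 0.2–3.5 points, or 0.1–1.9. Twelve-month PFS changes by −0.8 to +0.1 point.

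**5. Scale.** The 90% CI half-width for PFS is 1.645 x sqrt(0.36 x 0.64 / 25) = 15.8 points. For DoR it is 1.645 x sqrt(0.4 x 0.6 / n) = 20.1 points with 16 responders and 17.2 with 22 (65–87% of 25).

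**The case against.** - **Not every such progression is censored.** The protocol asks for prompt imaging on clinical suspicion and a scan at discontinuation. A progression found that way within 20 weeks of the last evaluable scan stays an event. This is right: censoring is certain only at the next scheduled scan in the 12-weekly phase. The unscheduled-detection runs allow for it, and they reduce the effect without removing it.
- **The footnote is the row's working definition.** A programmer would probably follow it, so rules may not compete in practice. That is fair for scan-detected progression, but the working definition then contradicts the estimand that it serves. A deliberately stricter rule is unlikely: the protocol's PFS censoring rules (9.4.3.4) contain no missed-scan rule, and SAP 3.9 lists no such change.
- **Large shifts in the median are a grid effect.** With 12-weekly scans the median moves in whole steps. In a run with exact scan dates and 10% missed, the curves at Week 69 were 50.2% and 48.5%, enough to move the median to Week 81. This stands, and the median shifts should carry little weight.
- **24 months is not a named landmark, and the schedule itself biases it.** With a 14.7-month median, true 24-month PFS is 32.2%, while scans with none missed give 36.4%, because Month 24 falls just before Week 105. This also stands. The excesses above are measured against the two-missed count, not against true PFS.
- **The endpoints are secondary and descriptive.** This is true and limits the consequence. The bias is nonetheless systematic and avoidable, and in late estimates it favours the treatment.

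**Conclusion.** The concern holds. The 20-week cut-off reproduces exactly on the 9-weekly schedule and fails on the 12-weekly one, using only the documents' own schedule. In 12-weekly imaging one missed scan always exceeds it; at the Week 45 transition it does so in 84% of in-window combinations.

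The size rests on the assumed missed-scan rates and exponential times. At the two Hodgkin lymphoma medians, 24-month PFS is 1.1–3.6 points too high with scheduled detection only and 0.6–2.0 with half unscheduled. Over assumed DoR medians of 9–24 months, 24-month DoR is 1.2–4.5 points too high, or 0.7–2.5.

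Median PFS changes by −0.9 to +1.2 weeks, except for +4.7 to +10.8 weeks with a 14.7-month median, no unscheduled detection, and either 15% missed or 10% missed with 20% per year stopping early. Median DoR changes by under 1 week if the true median is 9–12 months, and by +0.5 to +13.2 weeks if it is 18–24 months.

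All of this is well inside the confidence intervals. CRR, ORR and the primary cut-off at about 8 months are unaffected. It should be corrected because the rule contradicts the SAP's estimand.

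**What to change.** Replace the fixed gap in footnote c with a count:

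> Censor only if at least two assessments due under the imaging schedule in force were missed or non-evaluable between the last evaluable assessment and the documented progression or death.

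The same count then covers deaths. If a date rule is preferred, take the two scheduled dates that follow the last evaluable visit and censor only if the event is later than the second date plus 7 days:

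| Last evaluable scan | Next two due | Censor if event is after |
|---|---|---|
| Week 27 | 36, 45 | Week 46 |
| Unscheduled, Week 31 | 36, 45 | Week 46 |
| Week 36 | 45, 57 | Week 58 |
| Unscheduled, Week 40 | 45, 57 | Week 58 |
| Week 45 | 57, 69 | Week 70 |

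In the simulations where it was compared, this date rule matched the two-missed count to within 0.1 point.

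State also which schedule governs off treatment: 12-weekly from first IMP (master protocol 8.1.1) or 3-monthly from last IMP (4.1). The count cannot be programmed for that period until the two are reconciled.

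The cost is one footnote, that clarification and one programming rule that maps scans to scheduled visits. No new data are needed. Late PFS and DoR estimates may look slightly less favourable.
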